8.2 Secondary Endpoints

In addition to pooled analyses described above, separate analyses will be conducted for each skin type using a non-inferiority margin of 15%. The estimated risk difference in dichotomized DLQI at week 12 and PGA at or before week 12 will be estimated empirically based on the proportion of patients achieving the endpoint in each skin type sub-group and study arm. We will also assess heterogeneity of treatment effect (HTE) across the three skin types using logistic regression. In this analysis, we will fit models for each of the two primary outcomes with skin type, treatment arm, and their interaction as predictors. HTE will be assessed using an omnibus Wald test of all interaction regression parameters for each outcome of interest in order to minimize multiple testing and consequent alpha inflation.

In secondary analyses, we will investigate additional outcomes:

- Total number of phototherapy treatments received
- Cumulative dose of phototherapy
- Frequency of topical concomitant psoriasis treatment
- Changes in initiation, dosing, or discontinuation of oral or biologic psoriasis treatments
- Patient-reported amount of time spent on phototherapy
- Patient reported travel (cost and time)
- DLQI score of ≤1at week 12

- MCID on DLQI at week 1245
- Physician reported change in the product of body surface area (BSA) times PGA (both as a continuous measure and as a dichotomous measure evaluating a 75% and 90% reduction in the BSAxPGA).
- Duration of treatment response
- Percentage of patients receiving ≥ 80% of assigned treatments

Because we have no a priori hypothesis of equivalence between treatment arms on these outcomes, these analyses will be conducted using standard hypothesis testing principles. We will report the mean (for continuous measures) or frequency (for binary measures) and 95% CIs for each measure within treatment arms as well as the difference in means or frequencies between treatment arms and the 95% CI of the difference. Secondary outcomes will be measured with a frequency as described in Appendix D, Schedule of Study Procedures. We will analyze these measures using linear or logistic regression models with robust variance estimators via Generalized Estimating Equations (GEE) to account for within-patient correlation that occurs with repeated measures. Regression models will include terms for treatment arm, time since randomization (categorical), skin type, and the treatment arm/time interaction. Inclusion of the interaction term will allow us to assess possible variation in effectiveness of home phototherapy relative to office-based phototherapy over time. Physician reported outcomes (PGA times BSA) will be measured at baseline and at the earlier of week 12 or upon discontinuation of phototherapy, whichever comes first. We will compare this outcome between home and office-based phototherapy arms using linear regression adjusted for skin-type. All secondary analyses will be repeated within each skin type stratum.

During the follow-up observation period, weeks 13-24 after start of therapy, we will compare dichotomized DLQI, and receipt of concomitant topical psoriasis treatment between study arms. These measures will be assessed every four weeks during the observation period and analyses will use the same approach as described above for other secondary outcomes. We will also assess change in oral or biologic psoriasis treatment during the observation period at week 24.

Duration of response will be measured in patients who achieved a DLQI score of 5 or less at week 12, are no longer receiving phototherapy, and who have not initiated a new systemic treatment or had dose escalation of an existing psoriasis systemic treatment at any point during the study. Duration of response will be defined as the length of time from week 12 to the earliest of DLQI > 5 or time of initiation of a new systemic treatment or dose escalation of an existing systemic treatment, with patients who maintain DLQI \leq 5 throughout the 12 week observation period with no new systemic treatments or dose escalation censored at week 24. In order to obtain results that are generalizable to the full ITT study population, we will use inverse probability weighting to account for possible selection bias due to differences between characteristics of participants included in this analysis and the full study population. Duration of response will be analyzed using a Cox proportional hazards regression model adjusted for treatment arm, skin type, and their interaction. Based on results for the interaction term between study arm and skin type, we will report differences in duration of treatment response between study arms by skin type.

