3.1 General Design

The design is a large pragmatic randomized active comparator study of home vs. office based NB-UVB phototherapy for the treatment of psoriasis. Both comparator treatments are considered standard of care and thus this would be classified as a Phase IV study. Dosing of phototherapy will be based on a standardized protocol (see APPENDIX A) or a standard protocol that is routinely used by the local investigators in order to reflect routine clinical practice. The study will include up to 1050 patients stratified by Fitzpatrick skin type (350 skin type I/II, 350 skin type III/IV, we anticipate that approximately 80 participants will be enrolled in Skin type V/VI). We hypothesize that home phototherapy will be noninferior to office based phototherapy. There will be a recommended screening period of up to 28 days, to allow for obtaining informed consent and administrative procedures necessary for office based or home phototherapy, as well as randomization. Patients will be randomized (1:1) to home vs. office-based phototherapy within 28 days of the baseline visit or per standard of care of individual practices. If the patient is randomized to home phototherapy a machine will be delivered to their home and phototherapy treatment initiated within 14 days of randomization. If the patient is randomized to office phototherapy, the first treatment should occur within 14 days of randomization. The patient will be assessed by the dermatologist (or PA or NP or other gualified clinician as appropriate to the clinical practice) at baseline and at 12 (plus or minus 2) weeks after start of phototherapy, or at the time of discontinuation of phototherapy, whichever comes first. Patients will receive phototherapy treatments about 3 times per week for 12 weeks. They will then be observed for an additional 12 weeks. With each phototherapy treatment, patient response to prior phototherapy treatment will be collected by clinic staff or recorded on the phototherapy machine via patient assessment. Patients will complete a survey every 4 weeks for the duration of the study that captures patient reported outcomes.

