4.5 Total Number of Subjects and Sites

Recruitment will end when 1050 subject are randomized.

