6.1 Screening Period /Baseline Visit (recommended Day -28 to -14)

- Informed Consent/Assent
- Clinician measured PGA score
- Clinician measured BSA assessment
- Review Inclusion/Exclusion Criteria
- Demographics & Medical History
- Prior psoriasis medications and therapies
- Concomitant medications
- Patient reported DLQI
- Patient reported time spent on travel, cost of travel, (administered by the site)
- Patient reported target lesion image (staff assist for first image)
- Verify Insurance and record co-payment
- Inform participant of copayments
- Confirm patient's willingness to be randomized

Interim/ Set Up -14 to -1

- Randomize
- Prescribe and dispense home phototherapy machine for patients randomized to home treatment
- Schedule first phototherapy sessions, for patients randomized to office treatment

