We hypothesize that effectiveness of home-based UVB phototherapy will not be inferior to that of officebased phototherapy on either of the two primary effectiveness outcomes. At the conclusion of the trial we will report the response rate, i.e. the proportion of patients achieving clear/almost clear skin on the PGA at the earlier of 12 weeks after initiating home or office-based phototherapy or discontinuation of phototherapy and the proportion of patients with no to small impairment on quality of life (DLQI 0-5) at week 12 for each treatment arm with 95% confidence intervals. These measures will be reported for the complete study cohort and separately for two of the three skin type sub-groups. We will not be able to test the hypothesis of non-inferiority of home vs. office treatment in skin type V/VI. We will accumulate additional data in this group which will improve the precision of our estimates of efficacy in this patient population as well as gather additional data about barriers patients with skin type 5/6 face in accessing home or office base phototherapy that lead to inequities and health disparities in patients with psoriasis.

To account for stratification by skin type, which induces non-independence across strata, pooled analyses will be conducted using logistic regression adjusted for treatment arm and skin type. Skin-type adjusted risk differences between home and office-based phototherapy will be computed from odds ratios using marginal standardization. Statistical inference will be based on adjusted risk differences according to non-inferiority principles. Home-based phototherapy will be determined to be non-inferior relative to office based phototherapy if the lower bound of the adjusted two-sided 95% confidence interval for the risk difference is greater than the pre-specified non-inferiority margin of 15%.

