8.3 Sample Size and Power Determination

Our study has been powered to allow us to determine non-inferiority of effectiveness both overall and within two of the three skin type strata. Because a clinical question is whether effectiveness is equivalent within each skin type sub-group, our sample size has been determined in order to provide adequate power for these skin type-specific analyses. We have pre-specified two primary effectiveness outcomes and assume a type I error rate for each outcome at the one-sided alpha = 2.5% level which is standard for a non-inferiority trial and analogous to the more familiar two-sided alpha = 0.05. Although this alpha level does not explicitly account for multiple comparisons, we believe that doing so would be unnecessarily conservative as both our patient-reported and physician-reported outcome measures assess the same outcome and are expected to be very highly correlated⁴⁶. Assuming a 50% response rate in both the office based phototherapy group and the home-based group and a non-inferiority margin of 15% (i.e. the 95% two-sided confidence interval on the difference in response rates between office and home-based groups excludes 15%), we calculated that 175 patients of each skin type would need to be included in each study arm to have 80% power to establish non-inferiority of home based phototherapy at a one-sided significance level of 2.5%. In the pooled sample, we will have 99% power for a non-inferiority

margin of 15%. Our non-inferiority margin has been iterated with our patient research partners and expert dermatologists. It is well within previous suggestions of non-inferiority for psoriasis treatments⁴⁷. We also note that the FDA accepts a 15% margin or greater for the study of biosimilars of biologics for moderate to severe psoriasis^{48, 49}. Additionally, our estimates are more conservative (i.e., require a larger sample size) than the non-inferiority margin specified in the pragmatic trial of home versus office based phototherapy conducted in the Netherlands which only required 100 patients per group total³⁰. Our estimates require a larger sample size compared to the Netherlands study primarily because we have set a higher bar for effectiveness. Based on preliminary data, the rate of DLQI ≤5 is anticipated to be similar to the estimate of achieving clear or almost clear skin, providing 80% power for the same non-inferiority margin for this outcome¹⁵.

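### The skin-type I/II and III/IV non-inferiority tests use crude proportions; adjusting for the baseline PGA or DLQI already collected could raise their power (an improvement, not an error)

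*Combined protocol and SAP*

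**What the plan says.** Section 8.3 says that "our sample size has been determined in order to provide adequate power for these skin type-specific analyses", and that "175 patients of each skin type would need to be included in each study arm to have 80% power to establish non-inferiority". This assumes 50% response in both arms, a 15-point margin and one-sided 2.5%. Section 8.1 limits the skin-type tests to two of the three groups, because type V/VI will be too small.

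For those tests, section 8.2 says the risk differences "will be estimated empirically based on the proportion of patients achieving the endpoint in each skin type sub-group and study arm". Section 8.1 says that "pooled analyses will be conducted using logistic regression adjusted for treatment arm and skin type", followed by marginal standardization to a risk difference.

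The baseline visit (section 6.1) collects "Clinician measured PGA score" and "Patient reported DLQI", and section 6.1 places randomization after that visit. Neither is a covariate in any planned treatment comparison on the two primary outcomes. Section 8.4.4 does list plaque thickness, one of the three PGA items in section 7, as a possible influence on response, but only as an exploratory analysis. The linear regression for BSAxPGA in section 8.2 is adjusted for skin type and does not include the baseline value as a covariate.

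**The concern.** The tests that fix the sample size are also the least powered, and they set aside baseline information that is already in hand. At 80% power, each skin-type test misses true non-inferiority about one time in five. That rate was chosen and is not a mistake. It could be lowered without enrolling anyone or collecting anything further.

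The two skin types contain different patients. Treating them as independent, the chance that both succeed on one outcome is about 0.801 × 0.801 = 64%. What is at stake is the chance of reaching a clear answer in each skin type. The validity of that answer is not in question.

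**Working it through.** **Inputs from the documents.** Response is 50% in both arms, the margin is 0.15, alpha is one-sided 2.5%, and there are 175 patients per arm per skin type (section 8.3). Allocation is 1:1 (section 3.1). Section 4.5 says "Recruitment will end when 1050 subject are randomized", and section 3.1 says "we anticipate that approximately 80 participants will be enrolled in Skin type V/VI".

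**Input that is assumed.** R² is the share of outcome variance that the baseline value explains in enrolled patients. The documents do not give it. I use 0, 0.05, 0.10 and 0.20.

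**Formula.** With n patients in total, SE = √[0.5/(n/2) × (1 − R²)] and power = Φ(0.15/SE − 1.96).

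**Reproducing the plan.** For n = 350 and R² = 0, SE = √(0.5/175) = 0.0535. Power = Φ(2.806 − 1.96) = 80.1%. The stated 175 per arm and 80% are confirmed.

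**With baseline adjustment.**

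| Patients in the analysis | R² 0 | 0.05 | 0.10 | 0.20 |
|---|---|---|---|---|
| 350 in a skin type | 80.1% | 82.1% | 84.1% | 88.1% |
| 485 in a skin type | 91.0% | 92.4% | 93.6% | 95.9% |
| 620 in a skin type | 96.2% | 96.9% | 97.6% | 98.7% |
| 780 pooled | 98.7% | 99.0% | 99.3% | 99.7% |
| 1050 pooled | 99.8% | 99.9% | 99.9% | 100.0% |

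- 485 is (1050 − 80)/2, assuming an even split between types I/II and III/IV. 620 is what remains for one of them if the other stops at 350 (1050 − 80 − 350). 780 is 350 + 350 + 80.
- At 350 per skin type, the gain is worth 350/(1 − R²) = 368, 389 or 438 unadjusted patients.
- The chance that both skin types succeed on one outcome (independence assumed) goes from 64% to 67%, 71% or 78%.

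**Dropouts counted as failures (section 8.1).** This weakens the link between baseline and outcome. Assume overall response stays at 50% and dropout, at rate d, is unrelated to baseline. Response in completers is then p = 0.5/(1 − d), and the overall R² is (1 − d)² × R²(completers) × p(1 − p)/0.25. With a completer R² of 0.10:

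- d = 10%: 0.81 × 0.10 × 0.2469/0.25 = 0.08, power 83.3%.
- d = 20%: 0.64 × 0.10 × 0.2344/0.25 = 0.06, power 82.5%.

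**Simulation.** I compared the crude difference with logistic regression, marginal standardization and an influence-function SE, at 350 patients, with permuted blocks of 2 or 4 in 30 unequal clinics and 6000 trials per setting.

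| R² | Crude power | Adjusted power | Adjusted false non-inferiority |
|---|---|---|---|
| 0 | 79.9% | 80.0% | 2.2% |
| 0.05 | 79.0% | 81.6% | 2.3% |
| 0.10 | 79.8% | 84.6% | 2.4% |
| 0.20 | 79.1% | 87.5% | 2.2% |

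Monte Carlo error is about ±1.0 point on power and ±0.4 point on false non-inferiority. With 5% of baseline values missing and replaced by the mean (R² 0.10), power was 79.6% crude and 83.3% adjusted, with false non-inferiority 2.7%. A separate simulation of 10,000 trials per setting, without clinics, gave adjusted power of 82.5% at R² 5.6% and 88.8% at R² 23.5%, with false non-inferiority of 2.2% to 2.6%.

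**BSAxPGA, if analysed as absolute change.** Let k be the SD after treatment divided by the SD before, and ρ the correlation between the two. The SE with baseline as covariate, relative to the change score alone, is √[k²(1 − ρ²)/(1 + k² − 2ρk)]. For k = 1 and ρ = 0.3, 0.5, 0.7 this is 0.81, 0.87, 0.92. For k = 0.5 it is 0.49, 0.50, 0.48. Both k and ρ are assumptions.

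**The case against.** The strongest objection is that every figure beyond 80.1% depends on an R² that the documents do not supply, and several features could make it small. Entry requires a PGA above 1.0, which may narrow the baseline range. Dropouts and missing week 12 DLQI count as failures. The baseline visit may precede the first treatment by 28 days or longer plus up to 14 more. An R² of 0.20 needs a log-odds of 1.11 per SD, an odds ratio of about 3. All of this stands, so the lower part of the range is the safer expectation. It limits the size of the gain but does not create a loss.

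If recruitment runs to 1050, the skin-type tests may already have about 91% power, and adjustment adds only 1.4 points at R² 0.05 or 2.6 at 0.10. That also stands. With an uneven split, however, one skin type could still sit at 80%.

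The pooled test has almost no room to improve, so including it is for consistency. For BSAxPGA, baseline already enters through the change score, and the ratios above do not apply to the 75% and 90% reduction endpoints.

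Section 8.4.5 plans multiple imputation when missingness exceeds 10%, but for secondary and exploratory longitudinal measures. It does not contradict a simple rule for a baseline covariate. Finally, crude proportions are easy to explain and match the sample-size method. They can still be reported descriptively.

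**Conclusion.** The point holds as an improvement to a valid plan. At 350 patients per skin type, adjustment would cut the miss rate per test from about 20% to about 18%, 16% or 12% at R² 0.05, 0.10 or 0.20. With a completer R² of 0.10 and 10% to 20% dropout, the gain is 2.4 to 3.2 points. At 485 per skin type it is 1.4 to 4.9 points over the same R² range, and at R² = 0 it is nil. The results rest on 50% response in both arms, a true difference of zero and the assumed R². The false non-inferiority rate stays close to 2.5%, and the estimand and margin do not change.

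**What to change.** 1. For the separate skin-type I/II and III/IV analyses, pre-specify logistic regression with marginal standardization and a robust or bootstrap confidence interval. Use baseline PGA for the PGA outcome and baseline DLQI for the DLQI outcome. Use the same covariates in the pooled model, which keeps skin type. Retain the risk difference and the 15% margin.
2. Define baseline as the last value before randomization. Section 3.1.1 allows the baseline data to be collected again before that point. The week 1 DLQI in section 6.2.1 comes after open-label randomization and must not be used.
3. Replace a missing baseline value by the overall mean, without regard to arm, and state that this rule applies to these models.
4. Add baseline BSAxPGA to its linear regression in section 8.2.
5. Optional, for consistency with the stratified randomization in section 3.1.4: add clinic groups, merged by a pre-set rule, to the pooled model. In simulation this changed power by 0.2 points or less.

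The cost is a change of wording before unblinding. Because the text sits in section 8 of the combined protocol, it may need an amendment filed with the IRB. No new data are needed. The analysis becomes slightly more work, and there is no gain if baseline proves not to be prognostic.

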3.1.1 Screening Phase

Patients will be recruited from the sites' clinical practice. Patients being considered for phototherapy will be offered the opportunity to participate in this study at the discretion of the clinician. Electronic consent will be obtained before any study specific procedures are conducted. Electronic assent will be obtained from children eligible to participate and written consent will be obtained by their parent or authorized legal guardian. Consent and assent can be obtained remotely or in person.

The screening phase begins at the time of obtaining informed consent and continues until the patient is randomized (up to a total of 28 days or longer based on the local practice standard of care). The length of time between screening and randomization will be allowed to vary based on local practice standard of care as this is a pragmatic trial and thus we aim to reflect usual clinical practice. In usual practice, clinicians vary on the duration of time between when they evaluate a patient and when the patient actually starts phototherapy. This period can be delayed due to administrative issues (i.e., obtaining insurance approvals, etc), availability of phototherapy appointments, and patient schedule issues. The baseline visit will occur during the screening phase. Information collected at the baseline visit will be collected again if the patient sees the local provider again for routine care prior to randomization. The site will confirm that the patient is eligible for randomization by having obtained any insurance approvals necessary for office based treatment and confirming with the patient that they are willing to be randomized to office based phototherapy based on any additional information obtained from the insurance approval process (such as required co-pays or other cost sharing agreement). Patients are then randomized, and should receive their first treatment within 14 days of randomization.

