6.2 Study Intervention Phase Weeks 1-12

6.2.1 Week 1

- Administer NB-UVB phototherapy three times per week
- Patient reported DLQI (complete prior to first phototherapy treatment)
- Patient reported target lesion image taken prior to first treatment
- Patient reported psoriasis topical treatment
- Patient reported response to phototherapy prior to treatments. For those on office treatment, data is entered by the sites. For those on home treatment, data is recorded on the home device.
- Phototherapy session number and dose. For those on office treatment, data is entered by the sites. For those on home treatment, data is recorded on the home device

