8.4.5 Missing Data Strategy

Our analysis strategy for the primary outcome of clear/almost clear skin and the patient reported DLQI (no impact on quality of life) uses an ITT strategy by treating all patients who discontinue treatment prior to achieving clear/almost clear skin as treatment failures. Thus, for these outcomes there will be no missing data. For secondary and exploratory analyses of longitudinal outcome measures that require data from follow-up assessments, such as dosing of phototherapy, frequency of concomitant psoriasis treatment, and amount of time spent on treatment, our analysis strategy incorporates all available baseline and longitudinal information. The GEE estimator is only unbiased if data are missing completely at random (MCAR). If the total proportion of observations with missing data in a given analysis exceeds 10%, we will address loss of efficiency due to missing data and possible bias arising from violation of the assumption of MCAR missingness by undertaking multiple imputation (MI) implemented using multiple imputation via chained equations (MICE). Using MICE, we will create 10 imputed versions of the complete data set with all missing outcomes and patient characteristics imputed simultaneously. For each analysis that makes use of data elements with missingness, we will then conduct the analysis in each imputed data set and combine the results using standard rules.

We will conduct additional sensitivity analyses to explore the sensitivity of our results to possible missing not at random missingness. We will use the "tipping-point" approach to identify combinations of values for missing measures that would change the conclusion of our study and will summarize the results using graphical displays.

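### The secondary GEE model in 8.2 does not keep pre-treatment records out of its time levels, so its arm-by-time term would also respond to an effect that is constant once treatment has started

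*Combined protocol and SAP*

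**What the plan says.** Section 8.2 lists the terms of the GEE models for repeated secondary measures: "Regression models will include terms for treatment arm, time since randomization (categorical), skin type, and the treatment arm/time interaction". It gives the purpose of the last term: "Inclusion of the interaction term will allow us to assess possible variation in effectiveness of home phototherapy relative to office-based phototherapy over time". It does not list the time levels for each outcome. It refers instead to the schedule: "Secondary outcomes will be measured with a frequency as described in Appendix D, Schedule of Study Procedures". Appendix D appears only by title in the text available for review, so the visit lists in section 6 are the source here.

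Section 8.4.5 says of the longitudinal secondary analyses, naming concomitant psoriasis treatment among its examples, that "our analysis strategy incorporates all available baseline and longitudinal information".

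Section 6 shows which outcomes have an early record:
- **Travel.** The baseline list has "Patient reported time spent on travel, cost of travel, (administered by the site"), and travel is next asked at Visit 2.
- **Topical use.** "Patient reported psoriasis topical treatment" is listed at Week 1, then at Weeks 4 and 8 of the intervention phase. The Week 1 entry does not say whether it precedes the first session.
- **DLQI.** The Week 1 entry does say so: "Patient reported DLQI (complete prior to first phototherapy treatment").

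Randomization falls in the set-up window, days -14 to -1 (6.1), and app questionnaires run every four weeks from randomization (13.3). A record can therefore be after randomization and still before treatment.

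**The concern.** The question put to the interaction is whether the home-office difference changes over time. That question concerns the period when treatment is acting. If one time level precedes treatment, the interaction compares a level with no expected effect against levels where there may be one. It then responds to any effect, whether steady or changing.

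At stake is the interpretation of a secondary result. A steady difference in topical use could be described as a difference that varies over the course. Section 8.2 repeats the secondary analyses within each skin type, so the same reading could arise several times. The pre-treatment value would also go unused as a covariate, although it is already collected and would sharpen the later comparisons.

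**Working it through.** **Inputs from the plan.** The model terms are those of 8.2. Topical use is recorded at Weeks 1, 4 and 8 of the intervention phase; travel at baseline and Visit 2. Allocation is 1:1. Section 3.1 gives 350, 350 and about 80 by skin type, so (350 + 350 + 80)/2 = 390 per arm. The 1050 maximum gives 525 per arm, and one full skin-type stratum gives 175 per arm.

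**The plan's own figures.** No figure is given for the interaction. The sample-size basis in 8.3 reproduces:
- n per arm = (1.960 + 0.842)² × 2 × 0.5 × 0.5 / 0.15² = 7.849 × 0.5 / 0.0225 = 174.4, so 175 as stated.
- Pooled power = Φ(0.15/√(0.5/n) − 1.96) = 98.7% at 390 per arm and 99.8% at 525, against 99% stated.

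**What the interaction tests.** Let δ(t) be the arm difference in log odds at time t. No interaction over Weeks 1, 4 and 8 means δ(1) = δ(4) = δ(8). If Week 1 is pre-treatment and the arms do not yet differ, δ(1) = 0, and the hypothesis becomes δ(4) = δ(8) = 0: no effect at all. With Week 1 left out, the hypothesis is δ(4) = δ(8): a constant effect, which is the stated question. Travel has two levels, so the interaction is the Visit 2 difference minus the baseline difference, whose expectation is zero. It is simply the treatment effect.

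**Size, by hand.** The documents give no topical-use rates. Assume 60% in both arms at Week 1, 50% in the office arm at Weeks 4 and 8, a constant 10-point home difference at Weeks 4 and 8, 390 per arm, and a latent normal correlation of 0.5.
- Log odds ratio at Weeks 4 and 8: ln(0.6/0.4) = 0.405.
- Variance of the Week 1 log odds ratio: 2/(390 × 0.24) = 0.02137.
- Variance at Week 4 or Week 8: 1/(390 × 0.25) + 1/(390 × 0.24) = 0.02094.
- Approximate correlation between binary records: (2/π) arcsin 0.5 = 0.333.
- Variance of (mean of Weeks 4 and 8) minus Week 1: 0.02137 + 0.02094 × 1.333/2 − 2 × 0.333 × √(0.02137 × 0.02094) = 0.0212.
- Noncentrality: 0.405²/0.0212 = 7.7 on 2 degrees of freedom. Against the 5% critical value of 5.99, the rejection probability is about 70%.

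**Size, by simulation.** Same assumptions, latent correlation 0.5 to 0.75, two-sided 5% joint Wald test of the interaction terms, skin type omitted. The effect is constant at Weeks 4 and 8 in every non-null row.

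| Per arm | Constant effect | Rejects, Weeks 1, 4, 8 | Rejects, Weeks 4, 8 only |
|---|---|---|---|
| 390 | none | 4-6% | 4-6% |
| 390 | 5 points | 22-28% | about 5% |
| 390 | 10 points | 70-82% | about 5% |
| 525 | 10 points | 82-93% | about 5% |
| 175 | 10 points | 37-49% | about 5% |

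**Sensitivity to the assumptions.** A second set used a constant odds ratio, a pre-treatment level plus Weeks 4, 8 and 12, office rates of 20%, 35%, 45% and 50%, and latent correlation 0.5. For Week 12 differences of 5, 10 and 15 points, the test rejected in 15%, 48% and 87% of trials at 390 per arm, 18%, 63% and 95% at 525, and 9%, 25% and 51% at 175. Restricted to levels after treatment start, it rejected in about 4-6%. This layout matches no analysis listed in 8.2; it shows only how far the rate moves.

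**Value of the covariate.** At 390 per arm and a 5-point effect, adjusting the post-start comparison for the pre-treatment value raises power by about 6 points at correlation 0.5 (39% to 45%) and about 14 points at 0.75 (37% to 51%).

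**The case against.** The strongest reply is that the plan never says pre-treatment records are outcome rows. Time is measured since randomization, while 3.1.1 says "The baseline visit will occur during the screening phase", so a baseline record has no natural place on that scale. The sentence in 8.4.5 about baseline information belongs to a missing-data paragraph and could describe covariate use. This stands in part: the plan does not settle how these records enter. But 8.2 lists the model terms and includes no pre-treatment covariate, so on the listed model an outcome row is the only place left for such a value. The Week 1 record, moreover, does fall after randomization.

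Further points on the other side stand:
- Week 1 topical use is not labelled as preceding the first session. Patients also know their arm by then and might change their topical use, so a zero difference at Week 1 is an assumption.
- Section 8.2 names no test for this interaction. Its omnibus Wald test concerns skin type. Arm differences at each visit from the full interaction model remain valid, and 8.2 promises differences with confidence intervals.
- For travel, the two-level interaction is a legitimate estimate of the arm effect. Travel is also not a measure of effectiveness, so the harm there is mislabelling at most.

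A reader might go further and infer that the analysis is certain to report variation over time, or that the arm effect will be diluted by averaging over a pre-treatment level. The documents support neither. The first is a probability that depends on effect, correlation and sample size, and no averaging across visits is planned.

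**Conclusion.** The point holds as a gap in the specification with a definite consequence if the listed model is followed literally. Wherever a pre-treatment record is a time level, the arm-by-time term cannot separate a constant effect from a changing one. Under the assumed topical-use rates at 390 per arm, a joint test flags a constant effect in about 22-28% of trials for 5 points and 70-82% for 10 points, instead of about 5%. These rates rest on assumed use of 60% falling to 50%, latent correlation of 0.5 to 0.75, and no arm difference at Week 1.

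The reach is narrow: mainly topical use during the intervention phase, and travel time and cost. A DLQI model over Weeks 1-12 would also be affected, but 8.2 lists none. The primary non-inferiority analyses, BSAxPGA, the week-12-only DLQI endpoints, treatment counts and dose, time spent on phototherapy, and the weeks 13-24 analyses are untouched. It should not be read as a finding that the sponsor has decided to fit pre-treatment rows. The plan leaves that open, and the change below is worth making because it closes the gap with data already collected.

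**What to change.** In 8.2, for each repeated secondary outcome:
- List the time levels that enter the model.
- Where a pre-treatment record exists, enter the patient's own value as a covariate and not as an outcome row. State whether the Week 1 topical item is completed before the first session.
- Assess arm by time only across visits after treatment start, and report the arm difference with its confidence interval at each of those visits.
- For travel time and cost, compare the arms at Visit 2 adjusted for the baseline value, with no interaction term.

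This is a change of wording and needs no new data. The one cost is that patients without a pre-treatment value need it imputed. The planned MICE procedure can do this, but 8.4.5 starts imputation only above 10% missing, so the text should allow it for this covariate below that level too.
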